#### 1.2 DESIGN AND OBJECTIVES

#### STUDY DESIGN

This is a prospective, single-center, parallel group, open-label, randomized clinical trial, where we will investigate the efficacy of continuous positive airway pressure therapy (CPAP) in COVID suspected or confirmed patients who are sent home from the emergency room with mild pneumonia or respiratory illness but who do not require hospital admission. We propose a randomized controlled trial of CPAP (n=100) vs. control (n=100) in COVID-19 suspected or confirmed patients with pneumonia or respiratory illness. The overarching aim of this proposal is to determine if early use of CPAP at home will reduce the need for hospitalization or death in COVID-19 suspected or confirmed patients. We will include adult patients (age>18), oversampling when possible for obese patients who live alone or have more than one bedroom at home, with serologically confirmed or under investigation for acute COVID-19 infection, who have one or more of the following: fever (>38°C), sore throat, myalgia or flu-like illness AND have one or more of the following additional symptom or diagnostic criteria: abnormal chest xray, new onset cough, mild hypoxemia at rest (saturation less than 96%), abnormal lung exam, chest tightness or shortness of breath AND who are without need for hospital admission. Patients with preexisting pulmonary diseases such as advanced COPD, advanced parenchymal lung disease, history of pneumothorax etc. will be excluded (see inclusion and exclusion criteria for more information). Participants in both arms will be shipped a pulse oximeter to monitor oxygen

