
Aim 2: Younger Americans with COVID-19 infection have a higher rate of hospitalization and need for mechanical ventilation compared to younger citizens of other countries. One potential explanation is high obesity prevalence. Obstructive sleep apnea is present in over 50% of obese individuals and obesity further compromises lung compliance and ability to handle increased ventilatory demand seen in COVID-19 patients with related lung injury. Further, COVID infected individuals with OSA may be at higher risk for progression from mild pneumonia to ARDS however this remains to be determined. Therefore in Aim 2, we will determine if obstructive sleep apnea (OSA) is associated with increased hospitalizations and mechanical ventilation in COVID-19 suspected or confirmed patients. This will be achieved primarily through our control group (not receiving PAP therapy but will receive home sleep apnea testing). This is of vital importance as the primary treatment of OSA is CPAP and there are more than 8 million CPAP users in the United States. This treatment can therefore be leveraged to treat mild respiratory distress in COVID infected OSA patients in the face of a crisis with hospital and ventilator shortage. We hypothesize that obese patients with COVID-19 infection are more likely to be hospitalized or receive mechanical ventilation compared to non-obese individuals with COVID-19 infection. In exploratory analysis, we will also assess if OSA is an independent risk factor for hospital admission or death in our control group. We expect obesity and OSA to be correlated and will determine the independent impact of each of these on our primary endpoint.

**Aim 3:** To leverage EHR to determine a risk score to predict readmission to the Emergency room in COVID-infected or suspected patients. This aim will be done simultaneously while Aims 1 and 2 are ongoing and will be implemented in real-time to identify high-risk patients.

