#### **TIMELINE**

We anticipate that accrual will occur over a 1-3 month period, beginning as soon as IRB approval is obtained. The study will last until we have 100 participants in each group, and each group completes all phases of the trial.

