Early Continuous Positive Airway Pressure (CPAP) in COVID-19 Confirmed or Suspected Patients

PI: [name], MPH

NCT04390191

Document Date: 4-21-2020

General Design Issues

This is a prospective, single-center, parallel group, open-label, randomized clinical trial. The primary objective is to evaluate the efficacy and safety of the use of CPAP versus control in COVID-19 suspected or confirmed patients with pneumonia or respiratory illness. The primary efficacy endpoint is a **non-weighted composite endpoint comprised of the following components:**

- All-cause mortality within 14 days of randomization
- Hospital Admission (including ED visit) within 14 days of randomization
- Oxygen saturation less than 90 during the 72-hour observation period from randomization
- Absolute reduction in oxygen saturation of more than 4% during the 72-hour observation period from randomization

Sample Size and Power

Sample size was restricted by the availability of CPAP and the need for rapid answers during the exceptional health care challenges and fluid epidemiological conditions. The table below summarizes the effect sizes (% reduction in the proportion of patients with a negative outcome) that can be detected with sufficient power (>80%) under several scenarios assuming a total sample size of 200 patients (100 per arm) using a two-sided Fisher's exact test at the 0.05 significance level. Preliminary data from the Mount Sinai Health System indicated that about 25% of the COVID-19 positive patients with respiratory distress were sent home and subsequently hospitalized. We assumed that the proportion of patients with a negative outcome in the control group will range between 25% to 50%. Depending on these values, the planned sample size will allow us to detect a relative treatment reduction between 64% to 42% in this range (see table below).

Furthermore, given the short follow-up time for the assessment of the primary outcome and the nature of the primary outcome, we anticipate that we will be able to assess the primary outcome on all patients. We also believe that patients will be supportive of this intervention and compliant with treatment, so sample size was not adjusted for drop-out rates. However, if due to unforeseen circumstances we will conservatively set any missing primary outcome assessment to "negative" or "failure". Power calculations were performed in SAS 9.4 using the PROC POWER function.

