Proportion of patients with Negative outcome	Control	0.25	0.30	0.35	0.4	0.45	0.5
	СРАР	0.09	0.12	0.16	0.20	0.25	0.29
	Relative reduction in CPAP arm (%)	64	60	54	50	44	42

Randomization Design and Procedure

Patients will be randomized using a 1:1 allocation to CPAP versus control group. The randomization will be stratified by BMI ($\geq=30$ and ≤30), gender and age (≤60 , $\geq=60$). A random permuted block design will be employed, with random blocks of size 2 and 4.

Data Monitoring and Analysis

Primary Efficacy Analysis

The primary efficacy endpoint is the proportion of patients with a negative composite endpoint within 14 days of randomization and will be compared between CPAP and control groups. The null hypothesis is that the proportion of patients with a negative outcome will be the same between patients randomized to CPAP versus control arm. This hypothesis will be tested using a two-sided Fisher's exact test at 0.05 alpha level. The primary analysis will be conducted according to the intention-to-treat principle.

Early stopping rule: If three deaths are observed in the CPAP group, enrollment will be halted pending DSMB review and recommendations. As of April 03, the death rate for COVID-19 positive patients in NYC was 2.99% [95% Clopper Pearson CI= 2.986, 2.997]. The rate is expected to be lower for our patient population. As such, 3 deaths among 100 patients will indicate a proportion of 3% [95% CI: 2.57%, 3.78%].

Analyses of Secondary Endpoints

Safety

Safety analyses will be conducted according to randomization assignment and treatment actually received. Adverse event rates will be calculated as the ratio of the total number of events over 14 days divided by total patient-days at risk for the specific event from randomization. A Poisson model with robust variance estimation will be used to compare SAEs between CPAP and control patients.

Time-to-events outcomes

Time from randomization to event outcomes (Hospitalization or ED visit, ICU admission, intubation and mechanical ventilation) within 14 days of randomization will be compared between randomization groups using a log-rank test or Gray's test in the presence of competing risk of death. In addition, survival at days 14 and 28 post-randomization will be described by Kaplan-Meier curves and a log-rank test will be used to compare survival between the two groups.

Respiratory Function

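### Optional improvement, not an error: the primary Fisher's exact test leaves out the BMI, sex and age strata used for randomization

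*SAP*

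**What the plan says.** SAP, Randomization Design and Procedure: "The randomization will be stratified by BMI" (cut at 30), gender and age (cut at 60), which makes 2 × 2 × 2 = 8 strata. Allocation is 1:1, and "A random permuted block design will be employed, with random blocks of size 2 and 4".

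SAP, Primary Efficacy Analysis: "This hypothesis will be tested using a two-sided Fisher's exact test at 0.05 alpha level". The SAP names no stratified or covariate-adjusted primary analysis, and no effect estimate or confidence interval for the primary endpoint.

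SAP, Sample Size and Power: power is computed for the same unstratified test at 100 per arm, so design and analysis agree. On the number of patients: "Sample size was restricted by the availability of CPAP".

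Protocol 1.2, Aim 2: "We hypothesize that obese patients with COVID-19 infection are more likely to be hospitalized or receive mechanical ventilation". For obesity and sleep apnea, the investigators "will determine the independent impact of each of these on our primary endpoint". Protocol 1.2, Study Design, also plans "oversampling when possible for obese patients". The documents state no expectation for sex or age as predictors of outcome.

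**The concern.** Stratified randomization balances the arms on the chosen factors. If those factors predict outcome, the true variance of the treatment difference is smaller than an unstratified test assumes, so that test becomes more conservative than its nominal level. A stratified test recovers the difference. The sponsor randomizes on a factor it expects to matter (obesity) and then leaves it out of the primary test. Because the sample size is limited by equipment, any extra precision has to come from the analysis. At stake is a small amount of power and a slightly narrower interval; the validity of the result is not in question.

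**Working it through.** **Inputs from the documents.** 200 patients, 100 per arm, two-sided 0.05, the six control/CPAP rate pairs of the SAP table, 8 strata, blocks of 2 and 4.

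**Assumed inputs (not in the documents).** Shares of 50% obese, 50% of each sex and 40% in the older group; odds ratios of 1, 2 or 3 for each factor. The overall arm rates are held at the table's values, with one common treatment odds ratio across strata.

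**Step 1. Reproduce the SAP's power.** Power = Σ Bin(x; 100, p_CPAP) · Bin(y; 100, p_control), summed over all tables (x, y) that the test rejects. Exact results, in percent:

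| Control v CPAP | Fisher | mid-p | Pearson |
|---|---|---|---|
| 0.25 v 0.09 | 83.0 | 86.4 | 87.3 |
| 0.30 v 0.12 | 85.4 | 88.8 | 89.3 |
| 0.35 v 0.16 | 84.3 | 87.7 | 87.8 |
| 0.40 v 0.20 | 84.5 | 87.7 | 88.0 |
| 0.45 v 0.25 | 80.9 | 84.6 | 84.9 |
| 0.50 v 0.29 | 83.3 | 86.7 | 86.8 |

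The SAP's claim of more than 80% reproduces in every column. Over common event rates of 0.15–0.50, the exact size of Fisher's test is 3.3–4.0%.

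**Step 2. Simulate the planned randomization.** Permuted blocks of 2 and 4 were run within the 8 strata, 40,000 trials per cell. The arms come out exactly equal in 33% of runs. Protocol 1.3, Timeline ("The study will last until we have 100 participants in each group"), can be read as requiring 100/100, so that case was also examined by keeping only the runs with equal arms.

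CMH = [Σ(a_k − E_k)]² / ΣV_k, with E_k = n_1k·m_k/N_k and V_k = n_1k·n_0k·m_k·(N_k − m_k) / [N_k²(N_k − 1)]. The corrected version replaces |Σ(a_k − E_k)| by |Σ(a_k − E_k)| − 0.5.

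**Step 3. Split the gain.** CMH − Fisher = (CMH − Pearson) + (Pearson − Fisher). The first term is stratum information; the second is discreteness. For 0.45 v 0.25 under blocks, in percent:

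| Prognostic factors | Fisher | Pearson | CMH uncorrected | CMH corrected | Strata part | Discreteness part |
|---|---|---|---|---|---|---|
| none | 82.1 | 84.9 | 84.8 | 80.8 | −0.1 | 2.8 |
| obesity, OR 2 | 82.7 | 85.3 | 85.7 | 82.1 | 0.4 | 2.6 |
| obesity, OR 3 | 83.2 | 86.0 | 87.2 | 83.7 | 1.2 | 2.8 |
| all three, OR 2 | 83.3 | 86.0 | 87.5 | 84.1 | 1.5 | 2.7 |
| all three, OR 3 | 84.2 | 87.0 | 90.2 | 87.1 | 3.2 | 2.8 |

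**Step 4. Range over all six columns.** Strata part, in points:

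| Prognostic factors | Blocks, v Pearson | Blocks, v mid-p | 100/100, v Pearson | 100/100, v mid-p |
|---|---|---|---|---|
| none | −0.3 to −0.1 | 0.1 to 0.2 | −0.3 to 0.1 | −0.1 to 0.6 |
| obesity, OR 2 | 0.1–0.4 | 0.4–0.8 | 0.0–0.5 | 0.3–0.9 |
| obesity, OR 3 | 0.5–1.3 | 1.0–1.6 | 0.4–1.4 | 1.1–1.7 |
| all three, OR 2 | 0.7–1.5 | 1.1–1.8 | 0.6–1.6 | 1.3–1.9 |
| all three, OR 3 | 1.8–3.2 | 2.2–3.4 | 1.7–3.4 | 2.3–3.8 |

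The strata part hardly depends on how the allocation is read. The discreteness part does: 1.8–2.9 points under blocks, 3.1–4.6 at 100/100.

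**Step 5. Other shares.** With 30% or 70% obese and 10–40% older (strata down to about 3 expected patients), CMH minus Pearson is −0.4 to −0.1 (none), −0.2 to 0.5 (obesity OR 2), 0.2–1.2 (obesity OR 3) and 1.5–3.0 (all three OR 3).

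**Step 6. Size under blocks.** Fisher: 3.7–4.4% with no prognostic factor, 3.3–4.1% with obesity only, 2.4–2.9% with all three at OR 3. Uncorrected CMH: 4.8–5.2%, and 4.7–5.3% with the shares of Step 5.

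**Step 7. Continuity correction.** With no prognostic factor, corrected CMH under blocks gives 82.0, 85.0, 83.9, 84.2, 80.8 and 82.9%, below the exact Fisher power of Step 1 in all six columns. Uncorrected CMH gives 86.8, 88.8, 87.7, 87.6, 84.8 and 86.4%, above it in all six.

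**Step 8. Estimate.** Coverage of the Mantel–Haenszel risk difference (Sato variance), checked in two columns, is 94.7–95.0%. At 0.45 v 0.25 its mean 95% CI width against the unstratified width is the same with no prognostic factor (25.7 points), 24.9 v 25.7 with obesity OR 3, and 23.8 v 25.7 with all three at OR 3.

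**The case against.** The plan is valid, prespecified, consistent with its power calculation and adequately powered, so choosing another test is a preference. The gain rests on odds ratios that the documents do not supply. The obesity hypothesis concerns hospitalization or ventilation; ventilation is not a component of the primary composite, and two of its four components are saturation events. The treatment effect may also differ between strata, since CPAP pressure is set by sex and BMI. In simulations with obesity OR 2–3 in three columns, CMH minus Pearson is −0.1 to 0.7 if the log-odds effect is twice as large in obese patients, and 0.4–1.9 if twice as large in non-obese patients. If an assumed 10% of outcomes are missing and counted as failures, as the SAP prescribes, it is about −0.6 to 0.7. The change also gives up Fisher's guaranteed size for an asymptotic test. Finally, Protocol 1.5 requires DMC review and approval of substantive changes, so the administrative cost is more than a sentence of text.

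Most of this stands, and it is why the point is optional. The strata part may be zero or slightly negative even when obesity is prognostic, and the 1.7 is the top of a range, reached only against mid-p at exactly 100/100. None of it reverses the comparison with the planned test: these variations move the strata part by about a point or less, while Pearson leads Fisher by about 2–3 points under blocks, and the simulated size of uncorrected CMH stays near 5%.

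**Conclusion.** The point holds as a low-priority improvement. The primary analysis does not use the randomization strata, and the planned test is valid but conservative. The benefit specific to stratification is about 0 points of power if no factor is prognostic and about 0–1.7 if only obesity is, at an assumed odds ratio of 2–3. It reaches 1.7–3.8 if all three factors have an odds ratio of 3, for which the documents give no support. The further 2–4 points from replacing Fisher's test are a discreteness effect and no argument for stratifying. If no factor matters, stratifying costs at most 0.3–0.4 point against Pearson.

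**What to change.** Before any analysis of outcomes by arm:

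- Make the primary test a CMH test stratified by the randomization factors, stated explicitly as without continuity correction, and keep Fisher's exact test as a sensitivity analysis.
- Report a Mantel–Haenszel risk difference with 95% CI for the primary endpoint.
- Keep the power table, noting that it was computed for Fisher's test and is conservative for the uncorrected CMH test only.
- Write the strata as mutually exclusive and matching the REDCap randomization list. As printed, they share BMI 30 and age 60. This may be an artefact of text extraction and cannot bias the unstratified test, but a stratified test needs distinct cells. Protocol 1.2, Aim 1, already counts BMI 30 as obese, giving <30 and ≥30; the SAP should state once which side age 60 falls on.

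The cost is one or two SAP sentences, a check of the REDCap stratum definitions, and DMC review if the change counts as substantive under Protocol 1.5. No extra patients or data are needed: BMI, sex and age are already on the screening form.

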#### 1 - GENERAL STUDY INFORMATION

#### 1.1 INTRODUCTION

There is surge in COVID infected patients in New York City with a shortage of hospital beds, ICU beds and ventilators. Strategies to reduce the need for all of the above are immediately needed. Further, few interventions are targeted in COVID infected patients early in the course of their disease and especially in the community/home settings. Respiratory decompensation appears to occur later in the disease process (i.e. 7-10 days after becoming symptomatic) therefore many patients are sent home from the Emergency Room only to decompensate later at home. Some patients die at home and others are returning to the Emergency Room with advanced hypoxemic respiratory failure. There is no treatment offered to this population of patients, i.e. COVID suspected or confirmed and with respiratory symptoms or abnormal chest x-ray at the time of presentation. Based on experience across the globe, these patients are likely to worsen at home. We therefore propose a prospective, single-center, parallel group, open-label, randomized clinical trial to assess the efficacy of continuous positive airway pressure therapy (CPAP) (FDA approved and often used for treatment of sleep apnea) in COVID confirmed or suspected patients with abnormal chest x-ray or respiratory symptoms who do not require hospital admission and are discharged home from the emergency room. CPAP delivers positive pressure ventilation through a noninvasive facemask and can therefore be used at home. There is limited evidence on the use of CPAP for viral pneumonia resulting in acute respiratory distress syndrome (ARDS), as it offers no clear advantage over mechanical ventilation. However, in the last two decades, two viral pandemics (SARS 2003 and H1N1 2009) have triggered investigation into the use of CPAP due to severe shortage of mechanical ventilators. The success rate of CPAP was as high as 84% in H1N1 infected hospitalized individuals with lower severity of illness. Further, CPAP use in COVID-infected patients with respiratory abnormalities has shown promise in other countries such as England, China and Italy.

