## **Enrollment Eligibility Form:**

## **ER Admission Data Form**

*This is abstracted from the chart, data from the date of their admission to the ER prior to baseline
1. Date of admission to the ER:
2. Time of admission to the ER:
3. Number of days since symptom onset:
4. Source of COVID infection:

□ Unknown

□ Known

□ Occupational

□ Household
□ Other:
5. Did patient have any of the following symptoms (y/n):    Fever (y/n)   Cough (y/n)   Shortness of breath (y/n)   Chest tightness (y/n)   Sputum (y/n)   Nasal congestion (y/n)   Sore throat (y/n)   Chills (y/n)   gastrointestinal symptoms (y/n)
Vital signs in the ED
6. Temperature Fahrenheit:
7. Oxygen saturation:
□ Without supplemental oxygen
□ With supplemental oxygen
☐ How much supplemental oxygen?
☐ What method of oxygen: nasal canula, face mask, high flow nasal canula
8. Blood pressure:/
9. Pulse:

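### The primary analysis is an unadjusted Fisher's exact test; pre-specifying adjustment for ED oxygen saturation and days since symptom onset would be a cheap efficiency gain of uncertain size, not the repair of an error

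*SAP*

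**What the plan says.** The SAP (Primary Efficacy Analysis) compares the proportion failing the composite under intention to treat: "This hypothesis will be tested using a two-sided Fisher's exact test at 0.05 alpha level". It describes no adjusted, stratified or sensitivity analysis of this endpoint.

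SAP, Sample Size and Power, uses the same test, "assuming a total sample size of 200 patients (100 per arm) using a two-sided Fisher's exact test at the 0.05 significance level", and tabulates effects "that can be detected with sufficient power (>80%) under several scenarios". The stated result is that the trial can "detect a relative treatment reduction between 64% to 42% in this range", that is, for control failure proportions of 25 to 50%.

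The ER Admission Data Form (Protocol, Appendices) includes "3. Number of days since symptom onset" and "7. Oxygen saturation", the latter with a record of supplemental oxygen. Protocol 7.3 places this form at Visit 1, and Protocol 9.1 has randomization follow entry of all baseline data. SAP, Randomization Design and Procedure, stratifies by BMI, gender and age only.

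The documents give qualitative reasons to expect both variables to matter. Two of the four composite components are saturation events within 72 hours. Protocol 1.1 also states: "Respiratory decompensation appears to occur later in the disease process (i.e. 7-10 days after becoming symptomatic".

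**The concern.** Neither variable is balanced by design or used in the analysis. Any chance difference between arms in starting saturation or illness day therefore passes into the estimated effect, and outcome variation that these variables could explain stays in the error. The SAP says the sample size was limited by CPAP supply, so a more efficient analysis is one of the few ways left to gain precision. Timing matters too: in an open-label trial, an adjustment chosen after an imbalance has been seen is hard to defend, while one fixed beforehand is not.

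**Working it through.** **1. The SAP's own figure.** Inputs: 100 per arm, two-sided Fisher's exact test at 0.05, and the six pairs of rates in the SAP table. Full enumeration of all pairs of event counts gives:

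| Control / CPAP | 0.25/0.09 | 0.30/0.12 | 0.35/0.16 | 0.40/0.20 | 0.45/0.25 | 0.50/0.29 |
|---|---|---|---|---|---|---|
| Power, % | 83.0 | 85.4 | 84.3 | 84.5 | 80.9 | 83.3 |

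The claim of more than 80% holds in every column. The margin is small: a CPAP rate 0.01 higher gives 76.2 to 80.0%. The true size of the test, computed at the control rates, is 0.034 to 0.040, below the nominal 0.05.

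**2. Chance imbalance.** For a standardized covariate, the between-arm difference has SD sqrt(2/100) = 0.14, so its 95% range is about ±0.28 SD. The probability of a difference above 0.2 SD in either direction is 2 × [1 − Φ(0.2/0.1414)] = 0.16. For at least one of two independent covariates it is 1 − (1 − 0.157)² = 0.29.

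**3. Power with adjustment.** The documents give no prognostic strength, so it is assumed and varied. Two independent standard-normal covariates were given the same odds ratio (OR) per SD, with the SAP's marginal rates held fixed and 10,000 simulated trials per row. The gain from the covariates is adjusted minus unadjusted logistic regression (Wald tests). The total gain is adjusted logistic minus Fisher.

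| Rates | OR per SD | Fisher % | Unadjusted logistic % | Adjusted logistic % | From covariates | Total |
|---|---|---|---|---|---|---|
| 0.25/0.09 | 1.0 | 83.4 | 86.7 | 86.6 | 0.0 | 3.3 |
| | 1.25 | 82.7 | 86.2 | 86.7 | 0.4 | 4.0 |
| | 1.5 | 82.7 | 86.6 | 88.1 | 1.5 | 5.4 |
| | 2.0 | 83.4 | 86.6 | 90.4 | 3.8 | 7.0 |
| 0.40/0.20 | 1.0 | 84.2 | 87.3 | 87.1 | −0.2 | 2.9 |
| | 1.25 | 84.6 | 87.7 | 88.1 | 0.4 | 3.5 |
| | 1.5 | 84.3 | 87.7 | 89.6 | 1.9 | 5.3 |
| | 2.0 | 83.9 | 87.4 | 91.9 | 4.5 | 8.0 |
| 0.50/0.29 | 1.0 | 82.8 | 86.4 | 86.3 | −0.1 | 3.4 |
| | 1.25 | 83.0 | 86.5 | 86.9 | 0.5 | 4.0 |
| | 1.5 | 83.7 | 87.4 | 88.8 | 1.4 | 5.1 |
| | 2.0 | 83.2 | 86.5 | 91.1 | 4.5 | 7.9 |

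The standardized risk difference behaves similarly. Its covariate-only gain is 0.4 to 0.7, 0.6 to 2.3 and 4 to 5 points at OR 1.25, 1.5 and 2.0, and a further 3 to 5 points come from leaving Fisher. Its type I error was 4.9 to 5.6% in one set of runs and 5.4 to 5.9% in a separate set of 4,000 trials per cell.

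**4. What an imbalance does.** Take OR 1.5 and rates 0.40/0.20. In about 8% of trials the combined covariate score is more than 0.2 SD worse in the CPAP arm. In those trials the mean observed risk difference is 0.168 instead of 0.20, and power is 69% with Fisher against 89% adjusted (part of that gap is Fisher's conservatism). When the CPAP arm is healthier by as much, the mean difference is 0.228 and Fisher's power is 94%. The errors run in both directions and average out over randomizations.

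**5. How far the endpoint definition alone makes saturation prognostic.** If the fall is measured from the starting value s, a patient fails when it exceeds min(s − 90, 4). At s = 92 that is a fall of more than 2 points. At s = 94 and at every higher value it is more than 4. The mechanical gradient therefore exists only below 94%. With s spread over 92 to 99% and no other link to outcome, saturation adds 0 to 2 points. With s reaching down to 90% it adds 1 to 9, so the answer depends on an entry distribution that the documents do not give.

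**The case against.** The strongest reply is that nothing is broken. Fisher's test allows for chance imbalance in its null distribution, matches the sample-size method, needs no model and meets its stated power. All of that stands, and keeping an exact test primary in a rapid pandemic trial is defensible.

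The two covariates are also imperfect. The form holds chart data from the ER admission, taken before the trial baseline. Patients already discharged are eligible (Protocol 5.2), equipment may arrive 24 to 48 hours later (Protocol 7.1), and the outcome comes from a home oximeter. The ED value may have been taken on supplemental oxygen, and may be absent for patients denied entry to the ER (Protocol 2.3). The documents do not name it as the reference for the 4% fall. Symptom duration may relate to outcome non-monotonically: a patient at day 2 will pass through days 7 to 10 within the 14-day window, while one at day 12 is past them. In a simulation with days unrelated to outcome, 10% of ED values missing and only the mechanical saturation link, the covariates with both indicators changed power by −0.9 to +0.7 points, which is zero within simulation error.

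These points limit the expected gain and shape the model. They do not remove the case for it, because adjustment loses essentially nothing when the covariates are uninformative.

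**Conclusion.** The point holds as an optional improvement in efficiency and precision. Adjustment itself is worth about 0.5 point of power at an odds ratio per SD of 1.25 for both variables, 1 to 2 at 1.5, and 4 to 5 at 2.0. These strengths are assumptions, as are independent, normally distributed covariates with linear effects on the log-odds scale.

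A reader might infer three stronger claims that the documents do not support:

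- That the plan forfeits several points of power by omitting these covariates. This needs odds ratios near 2.0 for both. The larger totals against Fisher include 3 to 5 points that any less conservative unadjusted test would also recover.
- That saturation is strongly prognostic because of how the endpoint is built. The mechanical gradient stops at 94%, and a larger effect needs a clinical link that the documents do not quantify.
- That the test is invalid or the power table wrong. Type I error stays at or below 0.05, and the table reproduces.

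**What to change.** Before data are seen, add to the SAP a covariate-adjusted analysis of the composite: logistic regression on arm, ED saturation (continuous, with supplemental-oxygen and missing-value indicators) and days since symptom onset, in a stated functional form that allows a non-monotone relation. Report a standardized risk difference with a robust standard error. Either make this primary with Fisher's test in support, or keep Fisher primary and name this the key supportive analysis. State any expected gain as a range with its assumptions.

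The cost is SAP wording and a few lines of code, since the data are already on the form. There are three downsides:

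- If the model is primary, the test has size near 5% (5 to 6% in simulation) instead of Fisher's 3 to 4%.
- At 0.25/0.09 about 25 + 9 = 34 events are expected. Five non-intercept terms leave 34/5 = 6.8 events per term, and a second term for symptom days leaves 34/6 = 5.7, so the model should stay this small.
- The SAP must say how it handles ED values that are missing or were taken before the home baseline.

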- Improvement in oxygen saturation will be compared between randomization groups using linear mixed-effect models with patient as a random effect.
- Improvement in respiratory symptoms, as measured by the Clinical COPD Questionnaire, will be compared between randomization groups using linear mixed-effect models with patient as a random effect.

Conversion rate of family members

The conversion rates (yes/no) of family members in the two randomization groups will be compared using a Fisher's exact test. If there is sufficient variability, a zero-inflated count model may be considered as well.

Continuation of CPAP for greater than 72 hours

The proportion of patients in the CPAP group who elected to continue CPAP use after 72 hours will be estimated along with 95% Coppler-Pearson confidence intervals.

Exploratory Analyses

Exploratory analyses will be conducted similarly as the primary analysis except that it will be only in the control arm comparing OSA versus non-OSA patents and obese vs non-obese patients.

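### The 95% confidence interval printed for 3 deaths in 100 patients (2.57% to 3.78%) is really a 5% interval; the exact 95% interval is 0.62% to 8.52%

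*SAP*

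**What the plan says.** The early stopping rule stands in the SAP under Primary Efficacy Analysis. It reads: "If three deaths are observed in the CPAP group, enrollment will be halted pending DSMB review and recommendations". Three statements follow in support:

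- A benchmark: "the death rate for COVID-19 positive patients in NYC was 2.99% [95% Clopper Pearson CI= 2.986, 2.997" (per cent).
- An expectation for this trial: "The rate is expected to be lower for our patient population".
- The precision of the triggering result: "As such, 3 deaths among 100 patients will indicate a proportion of 3% [95% CI: 2.57%, 3.78" (per cent).

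Clopper-Pearson is named for the city interval; no method is named for the 3/100 interval. The denominator of 100 is the planned arm size (SAP, Sample Size and Power: "assuming a total sample size of 200 patients (100 per arm"). Later, under Continuation of CPAP for greater than 72 hours, the SAP plans the same kind of interval for the proportion who continue, which "will be estimated along with 95% Coppler-Pearson confidence intervals".

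**The concern.** Three events in 100 patients cannot fix a proportion to within about one percentage point at 95% confidence. A width of 1.2 points around 3% belongs to a sample of thousands.

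The interval is part of the SAP's written case for its only explicit stopping rule. As printed, it tells a DSMB member that three deaths place the CPAP-arm death rate between about 2.6% and 3.8%. Any lower rate that the sponsor expects, below about 2.6%, would then look excluded, and so would any rate above 3.8%. If the interval is far too narrow, neither exclusion is supported.

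If the cause is a wrong setting in a program, the same setting could also reach an interval that will be reported as a trial result.

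**Working it through.** **Inputs.** x = 3 deaths and n = 100 patients, both from the SAP sentence itself. Printed level and limits: 95%, 2.57% to 3.78%.

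**Formula.** Clopper-Pearson limits from beta quantiles:

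- lower = Beta quantile at a/2 with parameters (x, n − x + 1) = (3, 98)
- upper = Beta quantile at 1 − a/2 with parameters (x + 1, n − x) = (4, 97)

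**Step 1. Reproduce the printed figure.**

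| a | Confidence level | Lower | Upper |
|---|---|---|---|
| 0.05 | 95% | 0.623% | 8.518% |
| 0.94 | 6% | 2.547% | 3.801% |
| **0.95** | **5%** | **2.567%** | **3.778%** |
| 0.96 | 4% | 2.586% | 3.754% |

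Only a = 0.95 rounds to 2.57% and 3.78%. On a grid in steps of 0.0005, the values that match both limits run from 0.9495 to 0.951.

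**Step 2. Check against the binomial tails.** At a 95% limit each tail should hold 2.5%. With a true rate of 0.623%, P(3 or more deaths in 100) = 0.025; with 8.518%, P(3 or fewer) = 0.025. At the printed limits, 2.567% and 3.778%, both tails are about 0.475. Three deaths would be an unremarkable result at either limit, so the printed interval excludes rates that fit the data well.

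**Step 3. Try other 95% methods.**

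| Method, 95% | Interval for 3/100 |
|---|---|
| Wilson | 1.03% to 8.45% |
| Agresti-Coull | 0.65% to 8.83% |
| Jeffreys | 0.85% to 7.79% |
| Mid-P | 0.77% to 7.95% |
| Exact Poisson | 0.62% to 8.77% |
| Wald | 0% (truncated) to 6.34% |

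None is close. A larger denominator does not explain the figures either. At 95% with 3% observed, a lower limit near 2.57% needs about 5,300 patients and an upper limit near 3.78% about 2,300, so no single n gives both.

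**Step 4. Size of the error.** Correct width 8.518 − 0.623 = 7.895 points; printed width 3.78 − 2.57 = 1.21 points; ratio 7.895 / 1.21 = 6.5.

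**Step 5. The city interval (a query only).** The half-width is (2.997 − 2.986)/2 = 0.0055 points, or 0.000055 as a proportion. At a true 95% level the normal approximation gives n = 1.96² × 0.0299 × 0.9701 / 0.000055² ≈ 36.8 million cases. At a = 0.95, an exact search over whole numbers of deaths and cases reproduces both printed limits for n between 47,005 (1,406 deaths) and 64,020 (1,915 deaths). The SAP gives no counts, so this is consistent with the same slip but does not show it.

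**Step 6. What the setting would do to the CPAP-continuation interval.** Assume for illustration that 50 of 100 continue. At a = 0.05 the interval is 39.8% to 60.2%; at a = 0.95 it is 49.2% to 50.8%.

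**The case against.** The strongest reply is that nothing in the conduct of the trial depends on the interval. The trigger is a fixed count that leads to a review, not a test, and the SAP uses neither limit in any decision. The rationale can be read from the point values alone: a city rate of 2.99%, a lower rate expected here, and 3/100 = 3%. A pause for review does not need statistical separation from a benchmark, and the SAP claims none. The printed interval already contains 2.99%, so the correction changes nothing on that comparison. All of this stands, and it limits the point to the justification. It does not make the label right: the correction newly admits rates from 0.62% to 2.57% and from 3.78% to 8.52%, and the lower range bears on the sponsor's expectation of a rate below the city's.

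Three further reservations also stand in part:

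- **Cause.** That alpha was entered as 0.95 is an inference, though a close one. The interval is wrong whatever the cause.
- **City interval.** With the denominator unknown, many pairs of counts fit at a = 0.95 (the search finds 4,687), so a fit proves little. Only a request for the counts is justified.
- **CPAP continuation.** That analysis lies in the future, is planned at 95%, and nothing shows that it shares code with the printed interval. The SAP also states the 0.05 level correctly for the power calculation and the primary test. The 50/100 example is a reason for a check, not evidence of an error.

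**Conclusion.** The point holds. The interval printed as 95% for 3 deaths in 100 is not a 95% interval under any standard method tried. It equals the Clopper-Pearson interval at 5% confidence and is about 6.5 times too narrow. The correct exact interval, 0.62% to 8.52%, rests on no assumption beyond the SAP's own 3 and 100. It is compatible with a rate well below the city's 2.99% and with one nearly three times as high (8.52 / 2.99 = 2.8).

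The error lies in the support for the stopping rule, not in how the rule operates. It should be corrected because it misstates the evidence behind the only mortality trigger in the SAP. The city interval remains a query, and the CPAP-continuation interval needs only a precautionary check.

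**What to change.** 1. In the early stopping rule, replace the interval with 3% (95% Clopper-Pearson CI 0.6% to 8.5%) and name the method.
2. State the case and death counts behind the 2.99% city rate and recompute its interval at alpha = 0.05, or delete the interval.
3. Confirm that the program for the CPAP-continuation interval uses alpha = 0.05, and correct the spelling of the method there.
4. Optional: describe the trigger by the chance of reaching it. For 100 patients, P(3 or more deaths) is 8% at a true rate of 1%, 32% at 2% and 58% at 3%; the 1% and 2% rates are illustrative assumptions. The SAP could also note that a third death before full enrolment gives a higher and less precise estimate, for example 3/50 = 6% (95% CI 1.3% to 16.5%).

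The threshold itself is for the sponsor and the DSMB. The cost is a wording change in the SAP and one check of the interval code. The trigger, sample size, significance level and primary test are unchanged.
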